7.2.2.3 Analysis of Leakage

Distribution of leakage scores will be provided and proportion of injections with recorded leakage score >0 will be calculated per Pen Needles in each subgroup. Analysis as in Section 7.2.2.2 will be performed using the proportion of injections with recorded leakage score > 0 as response.

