3.3 Acceptance Criteria

Primary Objective: Non-Inferiority Criterion (based on relative VAS where -75mm indicates a strong preference for Period 1 pen needle and +75mm indicates a strong preference for Period 2 pen needle) is -10mm.

Secondary Objectives:

For Overall Comfort, Anxiety Associated with a Needle Stick Injury, Injection Pain, and Ease of Use the Non-Inferiority Criterion is also -10mm.

For Needle Breaking, Needle Bending, Injection Site Bleeding, Bruising and Leakage Score > 1: The difference in occurrence rate with BD Nucleus pen needle vs Occurrence rate with Current pen needle will be compared to a 4% non-inferiority (NI) criteria.

Exploratory Objectives: No formal acceptance criteria has been established for this study.

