Analysis for needle leakage: Distribution of leakage scores will be provided and proportion of injections with recorded leakage score > 1 will be calculated per pen needles in each subgroup. Same analysis as for needle breaking, needle bending, injection site bleeding or bruising will be performed using proportion of injections with recorded leakage score > 1 as the response. Exploratory endpoints will be summarized with proportion of “Yes” answers and 95% score confidence interval.

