3.5.2 Secondary Objectives

- Overall Comfort, Anxiety Associated with a Needle Stick Injury, Injection Pain, Ease of Use, Outer Cover Handling, Inner Shield Handling, Hub Comfort: Same as for primary objective
- Needle Breaking, Needle Bending, Injection Site Bleeding, Bruising and Leakage Score > 1: The difference in occurrence rate with BD Nucleus pen needle vs occurrence rate with Current pen needle will be compared to a 4% non-inferiority (NI) criteria.

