7.1.2 Leakage Scale

Needle leakage from the injections will be evaluated categorically according the droplet size at 6 different levels. Needle leakage is recorded using the 0 - 5 scale described in Figure 2. A binary leakage variable will be created with the equation below:

$$Y_{leak} = \begin{cases} \text{Yes, if recorded leak score} > 0 \\ \text{No, if recorded leak score} = 0 \end{cases} \quad (3)$$

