7.2.2.4 Analysis of Exploratory Objectives (Non-Comparative Questionnaire and Needle Breaking)

All the Exploratory binary responses (Yes / No) will be summarized with proportion of “Yes” answers and 95% confidence interval (score method) per pen needle group and overall.

In addition, for each pen needle group, a 95% confidence interval for the Proportion “Yes” with the BD Nucleus PN vs the Proportion “Yes” with the Current/Assigned PN will be calculated using the score method for independent proportions.

8 Safety Analysis

Data listings will be provided for any adverse events and serious adverse events in Appendix. The events will also be summarized descriptively per pen needle and study group. No safety analysis is planned.

9 Interim Analysis

Interim analyses will be performed for information only with no alpha adjustment.

10 Additional Analysis

A sub-group with Asian ethnicity, all study groups combined, will also be evaluated for the objectives listed in Section 3.2.1 and 3.2.2.

The primary endpoint may also be evaluated within each subgroups based on whether the patients had washout period before randomization.

11 Example Reports

This section provide examples of tables and graphical representations that will be provided in the study statistical report. These table examples were generated using the sample data available from the data base test framework which do not provide an exhaustive or representative example of the values and levels that will be obtained in the study. They are intended to provide illustrative examples of the tables and figures that will be included in the final statistical analysis report.

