11.2.3 Leakage from the Injection Site

The distribution of Leakage Scores per Pen Needle per subgroup will be provided as in Table 8 and Figure 7.

The leakage on a binary scale will also be presented and analyzed as in Section 11.2.2.

Table 8: Distribution of Leakage Score per Pen Needle per subgroup

Pen Needle	Score	Combined	Group 1	Group 2	Group 3	Group 4
BD Nucleus	0	62 (27.8 %)	18 (29 %)	5 (8.2 %)	9 (13.6 %)	12 (14.6 %)
	1	31 (13.9 %)	7 (11.3 %)	5 (8.2 %)	17 (25.8 %)	14 (17.1 %)
	2	43 (19.3 %)	5 (8.1 %)	12 (19.7 %)	14 (21.2 %)	7 (8.5 %)
	3	22 (9.9 %)	10 (16.1 %)	12 (19.7 %)	12 (18.2 %)	15 (18.3 %)
	4	47 (21.1 %)	9 (14.5 %)	18 (29.5 %)	5 (7.6 %)	20 (24.4 %)
	5	18 (8.1 %)	13 (21 %)	9 (14.8 %)	9 (13.6 %)	14 (17.1 %)
	Total	223	62	61	66	82
	All Score: >0	161 (72.2 %)	44 (71 %)	56 (91.8 %)	57 (86.4 %)	70 (85.4 %)
Current	0	85 (35.9 %)	20 (22.7 %)	7 (10.6 %)	6 (7.4 %)	14 (22.2 %)
	1	31 (13.1 %)	12 (13.6 %)	12 (18.2 %)	20 (24.7 %)	18 (28.6 %)
	2	39 (16.5 %)	16 (18.2 %)	6 (9.1 %)	8 (9.9 %)	8 (12.7 %)
	3	22 (9.3 %)	8 (9.1 %)	8 (12.1 %)	20 (24.7 %)	7 (11.1 %)
	4	44 (18.6 %)	19 (21.6 %)	18 (27.3 %)	7 (8.6 %)	5 (7.9 %)
	5	16 (6.8 %)	13 (14.8 %)	15 (22.7 %)	20 (24.7 %)	11 (17.5 %)
	Total	237	88	66	81	63
	All Score: >0	152 (64.1 %)	68 (77.3 %)	59 (89.4 %)	75 (92.6 %)	49 (77.8 %)

Figure 7: Barplots showing the Distribution of Leakage Score among the Injections per Pen Needle per subgroup

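### The 4% leakage criterion is set on score >1 in the protocol and in SAP 3.5.2, but the SAP derives, tests and reports score >0

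*SAP*

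**What the plan says.** Leakage is scored 0 to 5 after each injection and reduced to a yes/no response. The documents give two cut-offs.

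**Score >1**
- Protocol 3.3 attaches the 4% criterion to these responses: "For Needle Breaking, Needle Bending, Injection Site Bleeding, Bruising and Leakage Score > 1".
- Protocol 13.3 repeats the bleeding and bruising analysis "using proportion of injections with recorded leakage score > 1 as the response".
- SAP 3.5.2 restates the criterion, with 4%, for "Needle Breaking, Needle Bending, Injection Site Bleeding, Bruising and Leakage Score > 1".

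**Score >0**
- SAP 7.1.2: "A binary leakage variable will be created with the equation below". Equation (3) then codes Yes for any score above 0 and No for a score of 0.
- SAP 7.2.2.3 says the "proportion of injections with recorded leakage score >0 will be calculated per Pen Needles in each subgroup". It then sends the >0 response through SAP 7.2.2.2, which contains the rule that the upper 95% limit must be below 4%.
- SAP Table 8 has one summary row, for >0.
- SAP 11.2.3: "The leakage on a binary scale will also be presented and analyzed as in Section 11.2.2". That layout includes Table 7, with its pass/fail column at 4%.

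SAP 3.4.2 mentions a yes/no transformation without a cut-off. Nothing in the SAP derives or tests >1. Neither document explains the change, although Protocol 13.0 requires deviations from the original plan to be justified and described.

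Needle breaking has a related inconsistency. Protocol 3.2.2 treats it as secondary, and Protocol 3.3 and 13.3 and SAP 3.5.2 give it the 4% criterion. Protocol 2.3 and SAP 3.2.3, 3.4.3 and 7.2.2.4 place it among the exploratory items, for which Protocol 3.3 and SAP 3.5.3 and 11.2.4 apply no criterion.

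**The concern.** The cut-off defines the event being compared. A score of 1 is a non-event under the acceptance criterion and an event under the analysis, so the SAP as specified would judge one endpoint against a margin written for another.

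Protocol 1.0 and SAP 3.1 say that the outcomes are meant for marketing claims, and leakage non-inferiority is one of the planned conclusions. The study is open-label. SAP section 9 says: "Interim analyses will be performed for information only with no alpha adjustment", while Protocol 13.6 plans no interim analysis. With two cut-offs in writing, either result could later be presented as the prespecified one, including after data have been seen.

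**Working it through.** **Inputs.** Score counts from SAP Table 8; 4% margin from Protocol 3.3 and SAP 3.5.2; two-sided 95% score interval for two independent proportions from SAP 7.2.2.2. The plan's interval is used as it stands.

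**Interval.** With 1 = Nucleus and 2 = Current, it contains every d for which

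|p̂₁ − p̂₂ − d| / √V(d) ≤ 1.96, where V(d) = [p̃₁(1 − p̃₁)/n₁ + p̃₂(1 − p̃₂)/n₂] × N/(N − 1).

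Here p̃₁ = p̃₂ + d are the restricted maximum likelihood estimates and N = n₁ + n₂ (Miettinen-Nurminen form). Non-inferiority needs an upper limit below 4%.

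**Step 1: reproduce the SAP's own interval.** For 45/825 against 56/866 the SAP prints −0.01012 (−0.03303, 0.01273). The calculation gives the same.

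**Step 2: confirm which cut-off Table 8 uses.** Summing scores 1 to 5 reproduces all ten entries of the summary row. For Nucleus in Group 1, 7 + 5 + 10 + 9 + 13 = 44, or 44/62 = 71.0%. Score 1 is therefore counted as leakage.

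**Step 3: count the injections that change class.** Score-1 injections over the four groups:
- Nucleus: 7 + 5 + 17 + 14 = 43 of 62 + 61 + 66 + 82 = 271 (16%).
- Current: 12 + 12 + 20 + 18 = 62 of 88 + 66 + 81 + 63 = 298 (21%).

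**Step 4: run the test at both cut-offs.** Counts are Nucleus v Current; differences are Nucleus minus Current, in percentage points.

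| | >0 counts | Difference (95% CI) | 4% rule | >1 counts | Difference (95% CI) | 4% rule |
|---|---|---|---|---|---|---|
| Group 1 | 44/62 v 68/88 | −6.30 (−20.94, 7.70) | fail | 37/62 v 56/88 | −3.96 (−19.74, 11.62) | fail |
| Group 2 | 56/61 v 59/66 | 2.41 (−8.69, 13.41) | fail | 51/61 v 47/66 | 12.39 (−2.35, 26.71) | fail |
| Group 3 | 57/66 v 75/81 | −6.23 (−17.50, 3.79) | **pass** | 40/66 v 55/81 | −7.30 (−22.74, 8.20) | **fail** |
| Group 4 | 70/82 v 49/63 | 7.59 (−5.03, 21.03) | fail | 56/82 v 31/63 | 19.09 (2.93, 34.49) | fail |
| Combined | 161/223 v 152/237 | 8.06 (−0.48, 16.47) | fail | 130/223 v 121/237 | 7.24 (−1.87, 16.23) | fail |

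**Step 5: read the result.** The cut-off works in two ways. It moves the estimate, because the >0 difference equals the >1 difference plus the difference in score-1 shares. In Group 3 this is −7.30 + (17/66 − 20/81 = 1.07) = −6.23. It also changes precision. In Group 3 the interval is 3.79 + 17.50 = 21.29 points wide at >0 and 8.20 + 22.74 = 30.94 at >1, because the >1 proportions lie nearer one half. The flip there comes from precision, not from the estimate.

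**The case against.** The strongest reply is that the SAP's operative text is uniform: equation (3), 7.2.2.3 and Table 8 all say >0, and Protocol 13.0 leaves statistical detail to the SAP. This does not settle the matter. The SAP's own criterion in 3.5.2 says >1, and Protocol 13.0 also requires a justification that neither document gives.

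A second reply is that counting any leakage is simply stricter. That is not assured for a difference between needles: in mock Group 3, >0 is the lenient choice.

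Several points do stand:
- The counts are test data which, in the words of SAP section 11, "do not provide an exhaustive or representative example of the values". The Combined totals (223 and 237) do not equal the group sums (271 and 298), four of five rows keep their verdict, and the single flip rests on 3.79% against 4%.
- The full 0-5 distribution will be reported, so either result can be recomputed. That does not show which one was prespecified.
- The interim looks are labelled informational, so a choice made after seeing data is a possibility, not something shown.
- The descriptions of the scale levels are in a figure not reproduced in the text reviewed. Whether a score of 1 ought to count cannot be judged here. A justified move of the criterion to >0 would also be consistent.
- For breaking, only the pass/fail label is in doubt. The interval is produced either way (SAP 7.2.2.4), and every break is an adverse event under Protocol 9.2.

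**Conclusion.** The concern holds. The acceptance criterion names score >1 in three places, while the derivation, the test and the report use >0, with no reconciliation. In the mock data the choice reclassifies 16% of Nucleus and 21% of Current injections and reverses one verdict of five. That establishes that the conclusion can depend on the cut-off; it does not predict how often or in which direction in the trial. The documents give no expected leakage rate from which to estimate that.

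This should be corrected, but it is confined to a secondary endpoint and leaves the primary preference analysis untouched. The breaking inconsistency is real and smaller. It lies within the protocol as well as the SAP, because Protocol 2.3 makes breaking exploratory while Protocol 3.3 gives exploratory objectives no criterion and yet gives breaking the 4% one.

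**What to change.** **Leakage (SAP only)**
- In equation (3), code Yes for a score above 1 and No for a score of 0 or 1. State the same cut-off in SAP 3.4.2.
- Change both mentions in SAP 7.2.2.3 and the Table 8 summary row to >1.
- Keep >0 as a descriptive summary without pass/fail.
- Date the revision before any interim analysis or other comparative look at leakage by pen needle, not merely before database lock. Routine site checks of diary completeness do not count as such a look. If a look has already taken place, say so in the revision.

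The cost is a SAP revision and one line of derivation code, and the sponsor gives up a formal test at >0. If the sponsor prefers >0, it should justify the 4% margin for that event and amend Protocol 3.3 and 13.3 and SAP 3.5.2. The protocol changes need prior IRB/EC approval under Protocol 15.4.

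**Needle breaking**

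The sponsor should choose one status and state it throughout, on the same timing.
- Secondary with the 4% criterion: edit Protocol 2.2 and 2.3 and SAP 3.2.2, 3.2.3, 3.4.2, 3.4.3, 7.2.2.2, 7.2.2.4 and 11.2.4.
- Exploratory without it: edit Protocol 3.2.2, 3.3 and 13.3 and SAP 3.5.2.

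Either choice changes the protocol in substance, so Protocol 15.4 applies.

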7.2.2.4 Analysis of Exploratory Objectives (Non-Comparative Questionnaire and Needle Breaking)

All the Exploratory binary responses (Yes / No) will be summarized with proportion of “Yes” answers and 95% confidence interval (score method) per pen needle group and overall.

In addition, for each pen needle group, a 95% confidence interval for the Proportion “Yes” with the BD Nucleus PN vs the Proportion “Yes” with the Current/Assigned PN will be calculated using the score method for independent proportions.

8 Safety Analysis

Data listings will be provided for any adverse events and serious adverse events in Appendix. The events will also be summarized descriptively per pen needle and study group. No safety analysis is planned.

9 Interim Analysis

Interim analyses will be performed for information only with no alpha adjustment.

10 Additional Analysis

A sub-group with Asian ethnicity, all study groups combined, will also be evaluated for the objectives listed in Section 3.2.1 and 3.2.2.

The primary endpoint may also be evaluated within each subgroups based on whether the patients had washout period before randomization.

11 Example Reports

This section provide examples of tables and graphical representations that will be provided in the study statistical report. These table examples were generated using the sample data available from the data base test framework which do not provide an exhaustive or representative example of the values and levels that will be obtained in the study. They are intended to provide illustrative examples of the tables and figures that will be included in the final statistical analysis report.

11.1 Study Execution

The number of subjects enrolled, randomized, withdrawn, who completed and who are excluded will be provided as in Table 1. More details on specific data may be provided in Summary Statistics and Appendix.

11.1.1 Analysis Population Set(s)

Table 1: (PP) Population Disposition

Subject.Population	N	Comments
Subjects Enrolled	252	none
Subjects who did not meet I/E Criteria	6	none
Subjects Randomized	245	none
Subjects Withdrawn	5	none
Subjects who Completed the Study	240	none
Subjects Excluded from Analysis	1	Give Reasons

Table 2: Population per Subgroup - Randomized Subjects, with or without a wash-in period.

Pen Needle Group	No Wash-in	Wash-In	Overall
Group 1	66 (40.5%)	0 (0.0%)	66 (35.7%)
Group 3	33 (20.2%)	12 (54.5%)	45 (24.3%)
Group 4	28 (17.2%)	10 (45.5%)	38 (20.5%)
Group 2	36 (22.1%)	0 (0.0%)	36 (19.5%)
Total	163	22	185

11.1.2 Data Exclusions

All exclusions will be listed with reason(s) for exclusion.

11.2 Analysis and Results

11.2.1 Comparative Questionnaire (Relative VAS)

This section applies to all responses recorded on a relative VAS scale.

Summary statistics for each VAS scale will be presented as in Table 3.

The results for average relative VAS Score for BD Nucleus Pen Needle vs Current/Assigned Pen Needle will be evaluated per subgroup as presented in Table 4. The p-value for poolability will be provided in the caption (if the p-value < 0.05, then the results are not poolable across the groups). Results for all subgroups combined will only be presented if groups are poolable, otherwise only poolable groups will be combined. In the example in Table 4, all groups are poolable.

Table 3: Summary Statistics for 150mm Relative VAS Scores

Group	N	Mean	Std. Dev.	Mean 95% CI	Median	Median 95% CI	Q1	Q3	Range
Group 1	13	12.12	44.00	(-74.13, 98.36)	15.00	(-71.25, 101.25)	-15.00	60.00	-75, 67.5
Group 2	12	0.00	27.14	(-53.19, 53.19)	-7.50	(-60.69, 45.69)	-13.12	22.50	-37.5, 45
Group 3	9	-10.00	41.59	(-91.52, 71.52)	-22.50	(-104.02, 59.02)	-52.50	30.00	-52.5, 60
Group 4	10	-15.00	38.41	(-90.28, 60.28)	-37.50	(-112.78, 37.78)	-37.50	20.62	-52.5, 45
Combined	44	-1.88	38.38	(-77.11, 73.36)	-7.50	(-82.73, 67.73)	-37.50	30.00	-75, 67.5

Table 4: Average Relative VAS score for Nucleus vs Comparator PN table per Subgroup and overall (poolable groups). p-value for poolability = 0.7, all groups poolable

Pen Needle Group	Fitted Mean	CI	Non-Inferiority Conclusion (Lower bound CI > -10)	Superiority Conclusion (Lower bound CI > 0)
Group 1	28.3	(17.1, 39.4)	TRUE	TRUE
Group 2	19.2	(4.1, 34.4)	TRUE	TRUE
Group 3	26.1	(10.3, 42)	TRUE	TRUE
Group 4	18.7	(1, 36.4)	TRUE	TRUE
All Groups Combined	23.1	(15.5, 30.7)	TRUE	TRUE

Distribution of Relative VAS Overall Preference Scores with Average and 95% Confidence Interval

[figure not shown]

Figure 4: Distribution of relative VAS scores with average and confidence interval per pen needle group and overall. Positive scores indicate that BD Nucleus was preferred and negative scores indicate that the Current/Assigned PN was preferred.

[figure not shown]

Figure 5: Average relative VAS scores with confidence interval per pen needle group and overall. If the entire confidence interval is above -10, non-inferiority is demonstrated with 95% confidence and if the entire confidence interval is positive, Superiority is demonstrated with 95% confidence.

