13.3 Statistical Methods

All analyses will be performed and presented per subgroup (Group 1 – Group 4) first (with no alpha adjustment). For each response, a statistical test will be applied to determine whether it is valid to combine the results from the four study group into one overall result. If significant differences between the groups are identified, combined results will only include results from the groups exhibiting no significant difference; groups that are significantly different (if any) will not be grouped into the overall result.

If a sufficient number of subjects having a two-weeks wash-in period, are enrolled in the study, a comparison of the responses may be performed. The comparison will be conducted between the subjects who did wash-in and those who did not wash-in for all groups pooled together.

Descriptive statistics (number of observations, mean, standard deviation, minimum, maximum and 95% mean confidence interval) will be calculated and presented for all quantitative responses. Frequency tables with number of observations, percentage of total and 95% confidence interval (score method) for the percentage (as applicable) will be created for discrete responses.

Analysis for relative VAS: For each outcome measured on a relative VAS, a two-sided 95% confidence intervals will be calculated for the average rating. A modeling approach may be used to adjust for the visit effect (because of the often observed bias towards favoring the last PN used). Results will be tested for non-inferiority, followed by superiority:

If the lower bound of the CI is $> -10\text{mm}$, we can conclude in non-inferiority

If the lower bound of the CI is $> 0\text{mm}$, we can conclude in superiority

Analysis for needle breaking, needle bending, injection site bleeding, and bruising: A 95% confidence interval for the following difference in two independent proportions will be calculated using the score method:

$$\text{Proportion with BD Nucleus PN} - \text{Proportion with Current PN}$$

The upper bound of the confidence interval will be compared to the 4% NI criterion: non-inferiority will be concluded given the upper bound of the 95% score interval for the difference in proportions is $< 4\%$.

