3.5.3 Exploratory Objectives

No formal acceptance criteria.

4 Sample Size

Based on previous studies, SD for relative VAS is assumed to be 35mm. A sample size of 60 subjects per group has 90% power of passing a 10mm Non-Inferiority (NI) criteria, assuming a true average of 5mm in favor of Nucleus (2-sided 95% CI for the mean). A sample size of minimum 45 subjects per group is sufficient to provide at least 80% power (this lower sample size may be used for Group 2, Group 3 and Group 4). This sample size applies to each subgroup for which a NI (or superiority) claim is desired.

5 Intended Statistical Software

This document was generated with R version 3.3.2 (2016-10-31) and the following packages (version) were used: assertthat (0.1), base (3.3.2), BDbasics (0.1.11), colorspace (1.3.2), datasets (3.3.2), ggplot2 (2.2.0), graphics (3.3.2), grDevices (3.3.2), grid (3.3.2), gtable (0.2.0), lattice (0.20.34), lazyeval (0.2.0), magrittr (1.5), methods (3.3.2), munsell (0.4.3), nlme (3.1.128), plyr (1.8.4), Rcpp (0.12.13), reshape2 (1.4.2), rJava (0.9.8), scales (0.4.1), stats (3.3.2), stringi (1.1.2), stringr (1.1.0), tibble (1.2), tools (3.3.2), utils (3.3.2), xlsx (0.5.7), xlsxjars (0.6.1), xtable (1.8.2).

The study will be conducted within the same environment or more recent versions.

6 Data

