7.2.1 Summary Statistics

Summary statistics (number of observations, mean, 95% CI for mean, median, standard deviation and range) for all quantitative responses will be presented in tables. Frequency tables with number of observations, percentage of total will be created for all discrete responses. All summary and descriptive statistics will be provided per pen needle group and overall.

Bar plots may be provided for some responses.

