7.2.2.1 Analysis of Relative VAS Score

For each outcome measured on a relative VAS, a two-sided 95% confidence intervals will be calculated for the average rating. A modeling approach will be used to adjust for the order effect (because of the often observed bias towards favoring the last PN used). A linear model will be used to evaluate the pen needle group effect on the response to test whether the groups can be combined (a p-value < 0.05 for the pen needle group effect indicates non-poolability). In the model, the order of the pen needles used and the group to which the subject belongs based on their currently used or assigned pen needle will be used as covariates. LS means with CI will be obtained from the model and tested for non-inferiority, followed by superiority.

- If the lower bound of the CI is $> -10\text{mm}$, we can conclude in non-inferiority.
- If the lower bound of the CI is $> 0\text{mm}$, we can conclude in superiority.

Additional analysis: a *wash-in* indicator and an *Asian* indicator may be used to investigate these effects, as well as a site effect.

```
> #####
> ## Example R code to fit a linear model
> #####
> ##
> ## fitting the model
> model.fit=lm(vas_analysis ~ (NUCL_ORDER + PN_GROUP + ASIA)^2 + WASH_IN,
+             data=dataset, na.action=na.omit)
> #ANOVA table
> ## if p-value for PN_GROUP < 0.05, results not poolable across Groups
> anova(model.fit)
```

Analysis of Variance Table

Response: vas_analysis

	Df	Sum Sq	Mean Sq	F value	Pr(>F)
NUCL_ORDER	1	192	191.7	0.0928	0.7612
PN_GROUP	3	2757	919.0	0.4446	0.7215
ASIA	1	3215	3215.0	1.5554	0.2144
WASH_IN	1	751	750.8	0.3632	0.5477
NUCL_ORDER:PN_GROUP	3	3991	1330.3	0.6436	0.5882
NUCL_ORDER:ASIA	1	131	130.8	0.0633	0.8017
PN_GROUP:ASIA	3	308	102.6	0.0496	0.9853
Residuals	139	287317	2067.0		

```
> ##example contrast for the different pen needle groups
> ## given results not poolable,
> ## to identify which groups are not poolable
> ##
> model.fit=lm(vas_analysis ~ NUCL_ORDER + PN_GROUP,
+             data=dataset,
+             na.action=na.omit)
> ##
> library(multcomp)
> confint(glht(model.fit, linfct = mcp(PN_GROUP = "Tukey")))
```

Simultaneous Confidence Intervals

Multiple Comparisons of Means: Tukey Contrasts

```
Fit: lm(formula = vas_analysis ~ NUCL_ORDER + PN_GROUP, data = dataset,
na.action = na.omit)
```

Quantile = 2.5914

95% family-wise confidence level

Linear Hypotheses:

	Estimate	lwr	upr
Group 2 - Group 1 == 0	-9.0440	-33.6940	15.6060

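### SAP Table 3 labels estimate ± 1.96 × SD as a 95% confidence interval for the mean and for the median

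*SAP*

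**What the plan says.** SAP 11.2.1 opens with "This section applies to all responses recorded on a relative VAS scale" and continues "Summary statistics for each VAS scale will be presented as in Table 3". Table 3 gives, for Groups 1 to 4 and combined, the N, mean, SD, a 95% CI for the mean, the median, a 95% CI for the median, the quartiles and the range.

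The methods text says what should be reported. SAP 7.2.1 lists "Summary statistics (number of observations, mean, 95% CI for mean, median, standard deviation and range) for all quantitative responses". The list in Protocol 13.3 ends with "minimum, maximum and 95% mean confidence interval". Neither asks for a confidence interval for the median.

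The formal decision is made elsewhere. SAP 7.2.2.1 says "LS means with CI will be obtained from the model and tested for non-inferiority, followed by superiority", and Table 4 shows that output against the −10 mm and 0 mm limits.

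The introduction to SAP section 11 says the examples come from test data and are not representative. It also calls them "illustrative examples of the tables and figures that will be included in the final statistical analysis report".

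**The concern.** A confidence interval for a mean must narrow as n grows, and the intervals in Table 3 do not. The combined row (N = 44, SD 38.38) has a half-width of 75.24 mm; Group 4 (N = 10, SD 38.41) has 75.28 mm.

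Four of the five mean intervals run off the −75 to +75 mm scale at one end: Group 1 (98.36), Group 3 (−91.52), Group 4 (−90.28) and Combined (−77.11). Every median interval extends beyond the observed range in its own row, which an order-statistic interval cannot do. In Group 4, for example, the lower limit is −112.78 against an observed minimum of −52.5.

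At stake is the reporting of overall preference and the seven secondary relative-VAS endpoints. For each, the report would carry a descriptive interval labelled 95% CI that is far too wide and appears to disagree with the Table 4 interval for the same endpoint. SAP 3.1 says the outcomes are meant to support marketing claims, so intervals carrying that label need to be right.

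**Working it through.** **Inputs.** N, mean, SD, median and both intervals for each row of SAP Table 3; LS means, standard errors and 148 df from the example output in SAP 7.2.2.1; and, from SAP section 4, "SD for relative VAS is assumed to be 35mm" with a planned mean of 5 mm.

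**Step 1: reproduce the printed intervals.** Half-width = (upper − lower)/2, then divide by SD. For Group 1, mean: (98.36 + 74.13)/2 = 86.245, and 86.245/44.00 = 1.960. Directly, 12.12 ± 1.96 × 44.00 = (−74.12, 98.36); the table prints (−74.13, 98.36).

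| Row | N | SD | Half-width, mean | Half-width, median | Mean half-width / SD |
|---|---|---|---|---|---|
| Group 1 | 13 | 44.00 | 86.25 | 86.25 | 1.9601 |
| Group 2 | 12 | 27.14 | 53.19 | 53.19 | 1.9598 |
| Group 3 | 9 | 41.59 | 81.52 | 81.52 | 1.9601 |
| Group 4 | 10 | 38.41 | 75.28 | 75.28 | 1.9599 |
| Combined | 44 | 38.38 | 75.24 | 75.23 | 1.9603 |

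Estimate ± 1.96 × SD matches all ten intervals to within 0.02 mm, which rounding explains. Three alternatives match no row: z × SD/√n, t × SD/√n, and t × SD without √n.

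**Step 2: intervals for the mean from the same inputs.** Mean ± t(0.975, n−1) × SD/√n. For Group 1: 12.12 ± 2.179 × 44.00/√13 = 12.12 ± 26.59.

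| Row | Printed | t interval | Printed / t width |
|---|---|---|---|
| Group 1 | (−74.13, 98.36) | (−14.47, 38.71) | 3.24 |
| Group 2 | (−53.19, 53.19) | (−17.24, 17.24) | 3.08 |
| Group 3 | (−91.52, 71.52) | (−41.97, 21.97) | 2.55 |
| Group 4 | (−90.28, 60.28) | (−42.48, 12.48) | 2.74 |
| Combined | (−77.11, 73.36) | (−13.55, 9.79) | 6.45 |

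A proper median interval needs the raw scores and cannot be rebuilt from the table.

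**Step 3: planned sample sizes, SD 35 mm.** The Table 3 formula gives 1.96 × 35 = 68.6 mm at every n.

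| n | t half-width (mm) | 68.6 / t half-width |
|---|---|---|
| 45 | 10.52 | 6.5 |
| 60 | 9.04 | 7.6 |
| 240 (all groups poolable) | 4.45 | 15.4 |

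At a mean of 5 mm and n = 60, the correct interval is 5 ± 9.04 = (−4.0, 14.0), which lies above −10 mm. The Table 3 formula gives 5 ± 68.6 = (−63.6, 73.6). Its lower limit would clear −10 mm only if the mean exceeded 68.6 − 10 = 58.6 mm.

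**Step 4: is the decision interval affected?** LS mean ± t(0.975, 148) × SE for Group 1 is 28.278 ± 1.976 × 5.634 = (17.14, 39.41), as printed in SAP 7.2.2.1 and, rounded, in Table 4. The other three groups reproduce in the same way. These intervals are based on the standard error and are correct.

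**The case against.** The best case for leaving the table alone has four parts.

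- **The governing text is right.** An analyst who follows SAP 7.2.1 will compute a proper interval, and the reference to Table 3 can be read as fixing layout only.
- **Section 11 is test output, and parts of it are plainly placeholders.** In Table 13 the Group 3 mean age of 43 lies outside its own interval (28.35, 37.89), and the same five intervals appear for years since diagnosis and for years injecting insulin. In Table 8 the combined count for Nucleus score 1 is 31, while the groups sum to 7 + 5 + 17 + 14 = 43. Such output is weak evidence about production code.
- **No decision uses Table 3.** It has no criterion column, so the idea that a reader would take it as a failed non-inferiority test is conjecture. Quality control might well catch limits beyond ±75 mm.
- **The median column breaches nothing,** since no section requires a median interval.

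Much of this stands. It limits the consequence to reporting, confines the conflict with the methods text to the mean column, and leaves carry-over into the final report as an inference. It does not remove the error. Unrepresentative data can explain odd values of N, mean or SD, but not a wrong relation between them: a correct routine gives a correct interval from any data. One multiplier across ten intervals at five sample sizes points to a systematic formula, not placeholder noise. The SAP also says these are the tables the final report will contain.

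**Conclusion.** The point holds. It is certain that the Table 3 columns headed as 95% CIs contain estimate ± 1.96 × SD, and that the mean column is not the statistic SAP 7.2.1 and Protocol 13.3 require. The median column is a mislabelled extra that borrows the same width; its excess depends on the distribution of scores and is not quantified here.

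It is a strong inference, not a shown fact, that a summary routine with this formula would feed the final report. The planned-size figures assume that carry-over and the planning SD of 35 mm. The finding is limited to Table 3: Table 13 does not follow the pattern, and Figure 4 cannot be seen. Design, sample size and the non-inferiority and superiority tests are unaffected. It should be corrected because the statistic is required and the error would recur for every relative-VAS endpoint.

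**What to change.** 1. Compute the Table 3 interval for the mean as mean ± t(0.975, n−1) × SD/√n.
2. Either drop the median interval, which the methods text does not ask for, or keep it and state the method (order statistics or bootstrap) in SAP 7.2.1.
3. Check whether Figure 4 draws its intervals from the same calculation.
4. Regenerate the example table. A one-line note that Table 3 is descriptive and that conclusions rest on Table 4 would help the reader.

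The cost is small: a corrected calculation for two columns, or one if the median interval is dropped, and a rerun of the example. The exact code change cannot be given because the Table 3 code is not printed.
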